### **9.2.7 Complications of Influenza**

Complications of influenza are defined as pneumonia, myocarditis, worsening of chronic bronchitis, sinusitis, otitis, other chronic pulmonary diseases, encephalopathy, and death. Complications of influenza and use of antibiotic therapy for bacterial pneumonia will be reported by variable, treatment group, and time point. The number of subjects with a diagnosis of bacterial pneumonia/superinfection will be summarized by treatment group. Diagnosis of bacterial pneumonia will be based on local clinical practice, usually an assessment of clinical features and any radiographic evidence of bacterial pneumonia (e.g., infiltrate) and/or microbiologic evidence of bacterial pneumonia.

Sponsor-defined Bacterial pneumonia based on Medical History, Concomitant Medications and Adverse Events will be summarized. The definition of two Bacterial Pneumonia parameters will be based on the following criteria:

- (1) Incident Bacterial Pneumonia: defined as an adverse event of bacterial pneumonia or initiation of antibiotics Day 1 or after of greater than 2 days duration or an adverse event of pneumonia with concurrent use of antibiotics with the antibiotics initiated no more than 2 days prior to the pneumonia start date.
- (2) Any Bacterial Pneumonia: defined as Incident Bacterial Pneumonia or a medical history of bacterial pneumonia that is ongoing at time of enrollment or a medical history of pneumonia that is ongoing and being treated with antibiotics on the screening date.

All-cause and attributable mortality will be evaluated on Days 14, 28 and 56. Attributable mortality will be derived from the Complication of Influenza CRF; All-Cause mortality will be derived from Complication of Influenza, Seven-Level Ordinal Scale, Adverse Event and Study Completion CRFs.

Results of diagnostic laboratory tests (C-reactive protein (CRP), erythrocyte sedimentation rate (ESR) and procalcitonin results will be listed.

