6.1.2 Screening Procedures

Subjects will be given a full explanation of the nature of the study, provide full written informed consent before any study-specific assessments or procedures are performed, and undergo full screening procedures. Subjects will be assessed for inclusion and exclusion criteria, and those who fulfill all the inclusion and none of the exclusion criteria will be randomized into the study. A screen failure log must be maintained by the Investigator for all entry criteria failures. Table 1 lists the procedures performed at screening. Screening and baseline assessments (ie, Day 1 evaluations and procedures) may be performed on the same day.

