### 2.4.2 Secondary Objectives

Each of the following objectives will be assessed in the following pairings; 4000mg vs placebo, 2000mg vs placebo, pooled 4000mg+2000mg vs placebo and 4000mg vs 2000mg

January 17, 2019

- Among subjects requiring supplemental oxygen therapy at the time of enrollment with baseline room air oxygen saturation of  $\leq 92\%$ , time to cessation of oxygen (O2) support resulting in stable oxygen saturation (SpO2) by pulse oximetry. Stable SpO2 is defined as two consecutive SpO2 values of  $> 92\%$  on room air that are at least 8 hours apart.
- For any subject requiring supplemental oxygen therapy at the time of enrollment (regardless of oxygen saturation), time to cessation of oxygen support.
- Evaluate the effect of 2 dose levels of VIS410 + oseltamivir vs oseltamivir alone on the following parameters, also examine these outcomes in pooled VIS410 + oseltamivir arms vs oseltamivir alone:
  - Assess Viral load parameters in upper respiratory samples (MITT population and subsets)
  - Time to clinical response
  - Time to cessation of ventilator support
  - Time to resumption of normal activities
  - All-cause and attributable Day 14, Day 28, and Day 56 mortality rates
  - Clinical status ordinal scale mean area under the curve for Days 1-7 and Days 1-14 using linear numeric scores for the ordinal categories.
  - Comparison of clinical status ordinal scale scores
  - Comparison of clinical status ordinal scale scores using modified ordinal scale criteria (i.e., pooling of selected severity criteria scores)
  - Comparison of discrete ordinal scale parameters, including days of ventilator support, days in intensive care, and duration of hospitalization
  - Healthcare resource utilization
  - Analysis of time to alleviation of clinical signs and symptoms of influenza in the subset of subjects able to complete the Influenza Subject Reported Outcomes (FluPRO) Questionnaire at baseline and post-dose by Kaplan Meier analysis
  - Comparison of mean overall FluPRO scores by day and treatment arm, and mean FluPro Domain scores by day and treatment arm.
  - Proportion of subjects with newly documented bacterial pneumonia/superinfection
  - Proportion of subjects with influenza-related complications
- Pharmacokinetics of VIS410 in serum
- Immunogenicity of VIS410
- Emergence of resistance to VIS410 and oseltamivir

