  - Geographic region of enrollment
- Time to clinical response defined as resolution of at least 4 of 5 vital signs
  - Afebrile with core temperature ≤ 37.8°C, without use of antipyretics (oral ≤ 37.2°C)
  - Oxygen saturation ≥ 95% on room air without support or a return to pre-infection status, if pre-infection status was < 95%
  - Pulse rate ≤ 100/min
  - Systolic blood pressure ≥ 90 mm/Hg, without vasopressor use
  - Respiratory rate ≤ 24 beats per minute
- Clinical status ordinal scale mean area under curve for Days 1-7 and Days 1-14, using linear numeric scores for the ordinal categories.
- Comparison of clinical status ordinal scale scores for selected individual days (ie, Days 3, 4, 5, and 6)
- Comparison of clinical status ordinal scale scores using modified ordinal scale criteria (ie, pooling of selected severity criteria scores)
- Comparison of discrete ordinal scale parameters, including days of ventilator support, days in intensive care, and duration of hospitalization
- Number of days to resumption of usual activities
- All-cause and attributable mortality rates at Day 14, 28 and 56
- Total number of days in hospital and/or intensive care unit (ICU) from admission to discharge and rate of rehospitalization due to influenza A relapse/complication
- The incidence, severity, and duration of signs and symptoms of influenza-like illness as assessed by the FluPRO Questionnaire (see Appendix 16.3.1)
- The percentage of subjects with new bacterial pneumonia/superinfection

January 17, 2019

- The percentage of subjects with influenza-related complications
- VIS410 pharmacokinetic (PK) parameters in serum
- Titer of anti-VIS410 antibody positive samples
- Genotypic and/or phenotypic assessment to determine the emergence of VIS410 and oseltamivir-resistant viruses

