## 4.2 Missing Data Conventions

Partial and missing AE and concomitant medication dates will be imputed with maximum conservatism. If the onset date is missing or partial, the date will be compared as far as possible with the date of first dose of study medication. If no month is present and it is in the same year as the date of first treatment, or the year and month are the same as the first treatment date, the onset date will be imputed as the date of first treatment. Otherwise it will be imputed as 01 January in the available year, or the first day of the month and year available. End dates will be imputed as 31 December in the available year, or the last day of the available month and year collected. Partial dates will be presented in listings, along with classifications of TEAE for AEs or Prior/Concomitant/Both for medications.

Missing data will generally be left as missing, except for partial and missing AE and concomitant medication dates. Special cases, e.g. below the limit of quantification, will be described in the sections that describe the specific parameter's analysis.

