## 4.3 Subgroups

The following subgroups may be used to provide further information on the primary efficacy endpoint and other clinical and virologic endpoints:

- Use of positive pressure ventilation
- Use of endotracheal intubation
- Time from onset of symptoms to VIS410 therapy
- Number of oseltamivir doses prior to VIS410
- Age categorization (<65 years, ≥65 years)
- Presence of underlying chronic lung disease
- Presence of coincident pneumonitis (pneumonia) at baseline
- Influenza A subtype
- Enrollment geographic region: Tiered assessments: initially, dichotomous (Northern Hemisphere and Southern Hemisphere), then with each hemisphere broken into two groups: North America (Canada and US) and Europe (Belarus, Belgium, Bulgaria, Estonia, France, Georgia, Latvia, Russia, Serbia, Spain, Ukraine and Georgia); and Asia/Oceania (Australia, Malaysia, New Zealand, Singapore, and Thailand) and South Africa. Enrollment geographic region: (northern hemisphere vs southern hemisphere)
- MITT subset comprised of subjects with positive baseline viral cultures based on TCID50
- Baseline HAI titer category (to matched virus subtype) (≤40 or >40)
- Time between onset of symptoms of influenza and treatment (< 72 hours or ≥ 72 hours)

January 17, 2019

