### **6.3 Prior medications**

Prior medications are defined as medications that start before the study drug IV infusion. Prior medications will be coded with the World Health Organization Drug (WHODrug) Dictionary, Sep 2017 and summarized by Anatomical Therapeutic Chemical (ATC) Level 4, PT, and treatment in the ITT and MITT populations. A subject will only be counted once in an ATC class and an ATC class/PT combination. All eCRF medication data will be listed, including the WHO Drug ATC class, PT and the investigators verbatim description of the medication.

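### Incident Bacterial Pneumonia is met by any antibiotic course over 2 days begun on or after Day 1, so it does not measure new bacterial pneumonia

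*SAP*

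**What the plan says.** The secondary endpoint in SAP 3.2 is "The percentage of subjects with new bacterial pneumonia/superinfection", and the matching objective in SAP 2.4.2 is "Proportion of subjects with newly documented bacterial pneumonia/superinfection". SAP 9.2.7 summarizes local diagnoses of bacterial pneumonia. It then adds two sponsor-derived parameters built from medical history, concomitant medications and adverse events. The SAP's table of changes gives the reason for the addition: the complications eCRF had not been used correctly.

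The first parameter, Incident Bacterial Pneumonia, has three limbs joined by *or*. Limbs 1 and 2 are "an adverse event of bacterial pneumonia or initiation of antibiotics Day 1 or after of greater than 2 days duration". Limb 3 is a pneumonia adverse event with concurrent antibiotics begun no more than 2 days before it. The second parameter, Any Bacterial Pneumonia, adds pneumonia that was ongoing at enrollment to the incident cases.

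Four other rules bear on limb 2:

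- SAP 6.3 cuts at the infusion: "Prior medications are defined as medications that start before the study drug IV infusion". SAP 12.1 likewise splits infusion-day adverse events into before and after the infusion.
- Protocol 6.1.2 allows that "Screening and baseline assessments (ie, Day 1 evaluations and procedures) may be performed on the same day", and the schedule of assessments places baseline and predose within Day 1.
- SAP 4.3 lists "Presence of coincident pneumonitis (pneumonia) at baseline" as a subgroup.
- SAP 4.2 covers incomplete concomitant medication dates. For a start known only to fall in the infusion month, "the onset date will be imputed as the date of first treatment". For ends, "End dates will be imputed as 31 December in the available year, or the last day of the available month and year collected".

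**The concern.** Limb 2 alone is enough to make a subject an incident case, and it mentions neither pneumonia nor a reason for the antibiotic. A parameter named for incident bacterial pneumonia would then largely record antibiotic prescribing in hospitalized influenza patients on oxygen.

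The endpoint is secondary, and the study's stated purpose is to find candidate endpoints for Phase 3. Because the SAP itself says the eCRF behind the investigator count was misused, readers are likely to lean on the derived table (14.2.7.2). Suppose qualifying courses unrelated to new pneumonia occur equally in all arms. They then raise every arm's rate and shrink any real difference, and a useful endpoint could look insensitive. If they occur unequally, the contrast could move in either direction.

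**Working it through.** Neither document states an expected rate of bacterial pneumonia or antibiotic use, so there is no plan figure to reproduce. The check is a reading of the definition, followed by illustrations on assumed rates.

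**1. What each limb requires**

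| Limb | Pneumonia event needed? | Antibiotic condition |
|---|---|---|
| 1 | Yes, adverse event of bacterial pneumonia | None |
| 2 | No | Start on or after Day 1, lasting more than 2 days; no reason for use, no end of window |
| 3 | Yes, adverse event of pneumonia | Concurrent, begun no more than 2 days before the event |

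Limb 2 makes limb 3 nearly redundant. Limb 3 adds only courses of 2 days or less, or courses begun before Day 1.

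**2. Who meets limb 2 without new bacterial pneumonia**

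- A subject who starts antibiotics on Day 1 before the infusion. SAP 6.3 classes that course as prior medication.
- A subject with pneumonia at entry who starts a course on or after Day 1. The two-parameter structure implies that disease present at enrollment belongs only under Any Bacterial Pneumonia.
- A subject treated for another infection.

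A course with a known start before Day 1 does not meet limb 2.

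**3. Partial dates**

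Take a pre-study course with both day fields missing, in an infusion month of 30 days. SAP 4.2 sets the start to infusion date *d* and the end to day 30.

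- Start day counted: 30 − d + 1 > 2 holds for d = 1 to 28, that is 28 of 30 dates (93.3%).
- Start day not counted: 30 − d > 2 holds for d = 1 to 27, that is 27 of 30 dates (90.0%).

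These figures apply only when both days are missing. They do not say how often that happens.

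**4. Dilution**

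Let *p* be the true incidence and *a* the share of subjects with a qualifying course for other reasons. Assume *a* is the same in all arms and independent of true pneumonia.

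- Observed rate = 1 − (1 − a)(1 − p)
- Observed difference = (1 − a)(p₀ − p₁)

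With assumed p₀ = 10% and p₁ = 5% (4.0 and 2.0 of 40 per arm):

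| a | Observed rates | Difference | Risk ratio |
|---|---|---|---|
| 0% | 10.0% vs 5.0% | 5.0 points | 2.00 |
| 5% | 14.5% vs 9.8% | 4.75 points | 1.49 |
| 10% | 19.0% vs 14.5% | 4.5 points | 1.31 |
| 30% | 37.0% vs 33.5% | 3.5 points | 1.10 |
| 50% | 55.0% vs 52.5% | 2.5 points | 1.05 |

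At a = 30% the counts are 14.8 and 13.4 of 40. Other assumed rates shrink by the same factor: 20% vs 8% at a = 30% becomes 44.0% vs 35.6%, a difference of 8.4 points, which is 0.7 × 12.

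**5. What the flagged group consists of**

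At true incidence *q*, the share of flagged subjects with real disease is q / [q + a(1 − q)]. It falls below one half when a > q/(1 − q):

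- q = 5%: 5/95 = 5.3%
- q = 10%: 10/90 = 11.1%
- q = 20%: 20/80 = 25.0%

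**The case against.** The derived parameter is an added descriptive summary with its own table and no planned test. The SAP does not say it replaces the endpoint, and the local-diagnosis count is kept. A broad proxy is a reasonable response to a failed eCRF, the more so because Protocol 9.1.2 keeps influenza signs and symptoms out of adverse event reporting. The same SAP section speaks elsewhere of antibiotics for bacterial pneumonia, so that limit may have been intended. Baseline pneumonitis in influenza need not be bacterial, so a course begun after entry in such a subject may be exactly the superinfection sought. Protocol 7.6 and 8.1 call for dates of administration, not times, so Day 1 may be the finest cut available. All the rates above are assumed.

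Much of this stands as a limit on the consequences. The harm is to a descriptive table, its size is unknown, and a cut at the infusion may not be possible for every Day 1 course. The case of entry pneumonia shows why subjects with baseline disease should not be barred from later counting as incident.

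It does not rescue the wording. An intended indication that limb 2 does not state will not be programmed. The retained local count comes from the source the SAP calls unreliable. SAP 4.2 applies its date rule to concomitant medication dates in general, with no exception for this derivation.

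**Conclusion.** The definition is wrong as written. Followed exactly, it labels unrelated and pre-infusion antibiotic courses as incident bacterial pneumonia. That conflicts with the endpoint's restriction to new disease, with the SAP's infusion cut for prior medications and same-day adverse events, and with its own distinction between Incident and Any.

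Confidence in this reading is high. The size is not known. The shrinkage factor (1 − a) rests on unrelated courses being equally common in all arms and independent of true pneumonia, and the documents give no value for *a*. The point should be corrected before lock, but it threatens only a descriptive summary in an unpowered exploratory study.

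**What to change.** Amend SAP 9.2.7 as follows.

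1. Count a limb 2 course only if its recorded reason is pneumonia or lower respiratory infection **and** it began after the infusion.
2. First confirm what was collected. Protocol 7.6 requires reasons for use, but the field list in Protocol 8.1 omits them; check also whether start times exist. If reasons were not collected, make limbs 1 and 3 the main summary and report limb 2 separately as antibiotic initiation.
3. Where Day 1 timing relative to the infusion is unknown, or the start date was imputed under SAP 4.2, leave the course out of limb 2 in the main summary and include it in a sensitivity summary.
4. Put continuing treatment of pneumonia present at entry under Any Bacterial Pneumonia only. A later new course meeting item 1, or a new pneumonia adverse event, still counts as incident.
5. Report results by limb, with and without limb 2, and fix the classification before unblinding.

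The cost is SAP wording, a blinded review of antibiotic records before lock, and one extra summary. The drawback is that true cases with a vague indication or an unclear Day 1 start drop out of the main summary, and this loss need not be equal across arms. The sensitivity summary shows how much it matters.

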### **9.2.8 Nasopharyngeal Viral Load**

Standard non-compartmental approaches using Phoenix WinNonlin (Certara, Princeton, NJ, USA; Version 7.0 or higher) will be used to calculate nasopharyngeal viral load (VL) parameters. Viral load at each study visit, proportion of subjects with negative results at each study visit, peak VL, and VL AUC based on qRT-PCR and TCID50 from nasopharyngeal secretions will be summarized with n, mean, SD, geometric mean, CV, minimum and maximum values in the MITT population overall and per influenza A virus subtype. All available viral data within the MITT population will be assessed to calculate proportion of subjects with negative results at each study visit. For all other calculated parameters, viral load will be assessed on all samples in the MITT population collected through Day 7 for TCID50 and Day 14 for qRT-PCR.

January 17, 2019

Viral shedding by qRT-PCR or TCID50 versus time and VL AUC will be assessed using baseline-adjusted and non-adjusted comparisons. Each of the analyses described above will also be performed for the MITT subgroup comprised of all MITT subjects with a positive baseline-positive influenza viral culture result. In addition, VL and VL AUC by qRT-PCR for the first 50 subjects will be listed through Day 28 if subject is qRT-PCR positive on Day 14 and the Day 28 sample is tested by qRT-PCR (no summary statistics will be presented). For missing data on Day 1 post-dose, Day 3, Day 5 and Day 7, the analysis will be conducted without imputation and with the last observable measurement carried forward (LOCF). For missing data on Day 1 predose, the analysis will be conducted by replacing the missing data with the Day 1 postdose observable measurement. Subjects missing both Day 1 predose and Day 1 postdose will be removed from the analysis. Some parameters will also be analyzed using baseline-adjusted values. Viral load data will be normalized by dividing the value by the baseline value.

ANOVA will be used to assess the difference between treatment groups in the VL AUC from nasopharyngeal swabs based on qRT-PCR and TCID50. If the assumptions needed for ANOVA are not met, log transformation and/or non-parametric methods will be used. Differences between groups in peak post-baseline VL (qRT-PCR and TCID50) will be tested, and the proportion of subjects with peak VL (by qRT-PCR and TCID50) occurring post-baseline.

Several methods will be considered to assess the potential impact of baseline viral load (qRT-PCR and TCID50) on viral load AUC. Division of AUC by baseline viral load followed by ANOVA will be used as an initial measure of baseline viral load impact. In addition, an ANCOVA model may be used. The model will be evaluated with treatment as a fixed effect and baseline viral load as a continuous covariate. Each VIS410 dose group and the combined VIS410 total group will be compared to placebo.

Chi-square methods will be used to compare differences in treatment groups relative to placebo for the proportion of subjects with negative results on Day 3, Day 5 and Day 7 study visits.

For the influenza A virus subtype H3, virus load data measured by TCID50 will be read out by both hemagglutination and NP-ELISA. The sensitivity is higher for NP-ELISA; therefore, all viral load parameters will be calculated using the data from NP-ELISA only.

A list of viral load parameters in respiratory samples that may be assessed (MITT population and subgroups) includes:

- Peak virus concentration by qRT-PCR
- Viral nasopharyngeal qRT-PCR AUC, BL to Day 5 and BL to Day 7 (baseline-adjusted and non-adjusted comparisons)
- Viral shedding by qRT-PCR versus time (baseline-adjusted and non-adjusted comparison)
- Percentage of subjects in whom peak qRT-PCR value occurred post-baseline
- Viral nasopharyngeal qRT-PCR AUC, BL to Day 7 and BL to Day 14
- Peak virus concentration by TCID50
- Percentage of subjects in whom peak TCID50 value occurred post-baseline Viral nasopharyngeal TCID50 AUC, BL to Day 5 and BL to Day 7

January 17, 2019

- For TCID50 AUC analyses (both the MITT population and the MITT population subset comprised of subjects with positive BL nasopharyngeal viral cultures); baseline-adjusted and non-adjusted comparisons.
- Viral shedding by TCID50 versus time (baseline-adjusted and non-adjusted comparison)
- Percentage of subjects with negative viral cultures by nominal study day (Day 3, Day 5, Day 7) (both the MITT population, and the MITT population subset comprised of subjects with positive BL nasopharyngeal viral cultures)
- Kaplan Meier analysis of time to resolution (negative) of viral cultures, by treatment arm (both the MITT population, and the MITT population subset comprised of subjects with positive BL nasopharyngeal viral cultures)
- Additional subset analyses will examine the above outcomes by:
  - Virus strain family, H1N1 versus H3N2
  - Duration of symptoms prior to treatment (< 72 hours, ≥ 72 hours)
  - Geographic region of enrollment

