### 9.2.9 Handling of values below a threshold

For the calculation of qRT-PCR parameters, any value which is not recorded as a number but expressed as a value below a detection limit will be imputed by half the value of the declared detection limit itself. For samples reported as qRT-PCR negative the value will be imputed to zero.

qRT-PCR examples:

- If the database contains values like [REDACTED] will be used for calculating parameters.
- If the database contains values like “NEG”, zero will be used for calculating parameters.

For the calculation of TCID50 parameters, any value which is not recorded as a number but expressed as a value below a detection limit will be imputed to half the value of the declared detection limit for the first sample and the remainder values expressed as a value below a detection limit will be imputed to zero. qPCR negative samples that are not tested for TCID50 will be imputed to zero.

TCID50 example:

- If the database contains [REDACTED] the following rules will be used for calculating parameters
  - [REDACTED]
  - [REDACTED]

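### Setting negative samples to zero leaves the visit-wise geometric mean of viral load at zero, undefined, or limited to subjects still shedding; log-scale summaries need one stated positive floor

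*SAP*

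**What the plan says.** SAP 9.2.8 covers viral load at each study visit, proportion negative, peak viral load and viral load AUC, for both assays. These "will be summarized with n, mean, SD, geometric mean, CV, minimum and maximum values in the MITT population". The sentence does not list the median.

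SAP 9.2.9 then fixes the values of undetectable samples:

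- qRT-PCR, negative: "For samples reported as qRT-PCR negative the value will be imputed to zero".
- qRT-PCR, below the limit but not negative: "expressed as a value below a detection limit will be imputed by half the value of the declared detection limit itself".
- TCID50, below the limit: half the limit "for the first sample and the remainder values expressed as a value below a detection limit will be imputed to zero".
- TCID50, not run because PCR was negative: "qPCR negative samples that are not tested for TCID 50 will be imputed to zero".

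For the ANOVA of viral load AUC, SAP 9.2.8 adds a fallback: "If the assumptions needed for ANOVA are not met, log transformation and/or non-parametric methods will be used".

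Neither section gives a floor, offset or exclusion rule for a zero that enters a geometric mean or a log. SAP 11.1 does this for HAI titers, also summarised by geometric mean: values below 10 are taken as 5.

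**The concern.** A geometric mean needs strictly positive values. The plan asks for one at every visit and also fills the later visits with zeros, because samples turn negative as patients recover. The two rules can be reconciled only by a choice that the SAP does not make: keep the zeros and report 0, or drop them and report the subjects who have not cleared. If the CV is meant as a geometric CV, it has the same problem; the SAP does not say which kind it is.

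Ten by-visit viral load tables are planned (14.4.2.8.1.1 to 14.4.2.8.2.5). The trial's stated aim is to compare candidate endpoints for Phase 3, and viral load is one of them. If VIS410 works by clearing virus sooner, a positives-only geometric mean would show similar arms at the visits where they differ most. SAP 16.7 says that table shells follow once the SAP text is final, so the choice would fall to whoever programs the tables.

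**Working it through.** The documents give no figure on this point to reproduce. The check asks how the stated rules behave.

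**Inputs from the documents.** 40 subjects per arm, hence 80 in the pooled VIS410 group (SAP 2.1); the statistics in SAP 9.2.8; the zero and half-limit rules in SAP 9.2.9.

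**Assumed inputs.** The readable text gives no detection limit, negative rate or reporting scale, and the worked examples in SAP 9.2.9 are redacted. I assume negative rates of 2% to 60%, detection limits of 10^1 to 10^3, and positives centred at 5.0 log10 in every arm.

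**1. Effect of one zero.** Geometric mean = (x1 × x2 × … × xn)^(1/n). Any zero makes the product, and so the result, 0; ln(0) is undefined. This holds whether the stored values are raw or already log10.

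**2. How often a cell contains a zero.** P(at least one) = 1 − (1 − p)^n.

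| Negative rate p | n = 40 | n = 80 (pooled) |
|---|---|---|
| 2% | 55% | 80% |
| 5% | 87% | 98% |
| 10% | 98.5% | about 100% |

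**3. Dropping zeros versus a floor.** Take arms with 20% and 60% negative. In positives only, the geometric mean is 5.00 log10 in both, difference 0. With negatives at half the limit, the log10 geometric mean is (1 − p) × 5 + p × log10(limit/2):

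| Limit | log10(limit/2) | 20% negative | 60% negative | Difference |
|---|---|---|---|---|
| 10^1 | 0.70 | 4.14 | 2.42 | 1.72 |
| 10^2 | 1.70 | 4.34 | 3.02 | 1.32 |
| 10^3 | 2.70 | 4.54 | 3.62 | 0.92 |

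**4. The arithmetic mean in the same example.** On a log10 scale with zeros kept: 0.8 × 5 = 4.0 against 0.4 × 5 = 2.0. On the raw scale, with every positive at 10^5: 80,000 against 40,000. The difference is visible either way.

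**5. When AUC is zero.** Use the trapezoidal rule with samples at 0, 2, 4 and 6 days for illustration. Baseline 5 and then all zeros gives ½ × (5 + 0) × 2 = 5. A TCID50 profile that is below the limit throughout, with the first value at an assumed half-limit of 0.5, gives ½ × (0.5 + 0) × 2 = 0.5. AUC is 0 only if every sample is 0. Peak post-baseline load needs less: it is 0 when all post-baseline samples are 0, whatever the baseline.

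**The case against.** A reader might go further and infer that the viral load tables cannot show an effect, that the plan hides clearance, or that the log-scale ANOVA would discard subjects who have cleared. The documents do not support these readings.

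- **Tables.** The same sentence in SAP 9.2.8 asks for the arithmetic mean and SD, which keep every zero, and for the proportion negative at each visit.
- **Clearance.** SAP 9.2.8 plans chi-square tests of the proportion negative at Days 3, 5 and 7. SAP 9.2.10 plans Kaplan-Meier time to resolution for both assays, with log-rank tests.
- **Log fallback.** It is attached to the ANOVA of viral load AUC and has a non-parametric alternative, which can handle zeros. An all-zero profile is possible, since SAP 6.1 allows influenza A to be confirmed by methods other than PCR, but it should be uncommon.
- **Median.** SAP 4.1 lists it for continuous parameters in general, and Figures 14.4.1.1 and 14.4.1.5 plot median shedding. It is absent from the specific list in 9.2.8, not from the whole plan.
- **Scale.** If values are stored as log10 (an assumption), zero acts as a floor of 1 unit, and the planned arithmetic mean is already the log of a geometric mean with that floor.
- **Nature of the fix.** One floor merges PCR-negative with detected-below-limit, which SAP 9.2.9 keeps apart, and the result depends on the limit.

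All of this stands, and it narrows the point. It does not supply the missing rule: the geometric mean that the SAP asks for is degenerate on either scale.

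**Conclusion.** The point holds for the visit-wise geometric mean of viral load, and for a geometric CV if that is what is meant. Under the stated rules this statistic is zero or undefined once any subject in the cell has a zero, or else describes only subjects still shedding. It therefore cannot show a treatment difference in clearance. At a 5% negative rate, 87% of cells with 40 subjects would be expected to contain a zero. In the illustration, a true separation of 0.92 to 1.72 log10 becomes none in positives only. These sizes rest on assumed negative rates, detection limits and equal positive levels.

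The log fallback for AUC is affected only when all of a subject's samples are zero. A log-scale analysis of peak post-baseline load, for which SAP 9.2.8 plans a test without naming a method, would be affected somewhat more often. Clearance is still tested directly elsewhere, and the primary endpoint is not involved. This is a specification conflict in a secondary summary that should be corrected; it does not undermine the virology plan.

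**What to change.** In SAP 9.2.8 and 9.2.9:

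1. State the reporting scale of each assay, unless the redacted examples already do. It also settles what half the limit means: with a limit of 10^2, half on the raw scale is 50 (1.70 log10), but half of 2 log10 is 1.0.
2. For geometric means and any log-scale test, give every negative and below-limit sample one common positive floor at all visits, for example half the detection limit, as SAP 11.1 does in kind for HAI titers. The zero rule can stay for the other summaries.
3. Add median and quartiles to the viral load tables.
4. Print the proportion negative beside each geometric mean.

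The cost is SAP wording and one derived variable, with no new data. The small downside is that the geometric mean then depends on the chosen floor, so each table should footnote it.
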